#### Power:

Effect sizes, calculated based upon pilot data, are large for testing of main hypotheses. For example, the mean difference in AMYG volumes between BD and HC subjects was 382 ml, corresponding to an effect size of 1.14. Mean reductions in volume in the OFC ROI of 3.35±1.73% in BD subjects compared to reductions of 0.78±3.40% in HC subjects. The absolute difference of 2.57 corresponds to a standardized effect size (d) of 0.93. A sample size of 50 subjects per group will provide >95% power to detect differences of this magnitude even at attrition rates as large as 30%.

## SECTION IV: RESEARCH INVOLVING DRUGS, DEVICES OR BIOLOGICS

Please note: protocols using chemicals, hormones, other natural substances, or devices not regulated by the U.S. Food and Drug Administration (FDA) must still complete this section of the application form. Based upon the information provided in items 1-4, the HIC will determine whether an Investigational New Drug (IND) or Investigational Device Exemption (IDE) application must be submitted to the FDA.

This section is not applicable to this study.

### **SECTION V: HUMAN SUBJECTS**

1. **Recruitment Procedures:** How will potential subjects be identified, contacted and recruited? Attach copies of any recruitment materials – such as flyers, telephone scripts, or introductory letters that will be used.

Please note that a researcher may not use an individual's Protected Health Information (PHI) for recruitment into research without first obtaining an authorization from the individual, or a Waiver of Authorization from the HIC. A treating provider does, however, have the option to:

- Discuss with his/her own patients the option of enrolling in a study.
- Obtain written authorization from the patient for referral into a research study.
- Provide background information about the study to the patient so that the patient can initiate contact with the researcher.
- Provide the individual's PHI to a researcher without authorization when the researcher has obtained an approved Waiver of Authorization for recruitment purposes from the HIC.

If PHI will be accessed without subject authorization, please state whether any member of the research team has an existing clinical relationship with the potential subject. Researcher-clinicians are

permitted to access the PHI of their own patients, or patients of co-investigators listed on the protocol, for recruitment purposes. Alternately, please submit a completed Yale University Request for HIPAA Waiver of Authorization for Research Form (available at http://info.med.yale.edu/hic/hipaa/. For further information, see the Yale HIPAA website at http://info.med.yale.edu/hipaa/.

Overall Recruitment Efforts: Through a variety of efforts, subjects will be informed about our study. These efforts will include educational presentations, and websites (e.g. Craig's List, FaceBook, YCCI website, and the Yale University Department of Psychiatry website).

The flyers will be widely distributed (e.g., within school systems given prior authorized permission to do so) and placed at varied locations throughout the community. We will also be sending out information packets to area clinicians in private practice, group practices, community agencies, and public-school systems (e.g. school counselors).

Potential subjects or their referrers may call the research staff directly. A telephone screen is administered with the study procedures and potential risks and inclusion and exclusion criteria explained in detail over the telephone to the referrer or parent/guardian and the child. If eligible and interested, an in-person appointment will be scheduled to obtain written informed consent and assent. If the parent/guardian agrees to consider having their child participate then a follow up in-person appointment will be scheduled to obtain written informed consent and assent.

Additional Methods of Recruitment of Individuals with Mood Disorders and/or ADHD: Study inclusion and exclusion criteria and procedures will be discussed with clinicians from the Yale Medical Center and the Yale Child Study Center (CSC) as well as treaters in the surrounding community. We will recruit through referral sites of the CSC including satellite programs such as Cedarhurst therapeutic school and affiliated hospitals throughout CT, including Bridgeport Hospital. We have clinicians who are collaborators on both inpatient and outpatient adolescent and young adult clinical programs of Yale New Haven Psychiatric Hospital. We will provide written information about the study to inform them, and so that they may provide the written materials to parents/guardians of potential subjects. The parent/guardian would then be able to contact the research staff directly. However, if the treating clinician is one of the study investigators, the treating clinician will be able to enroll the participant directly. Participants may also call the research coordinator after viewing the HIC approved advertisement for this study.

Additional Methods of Recruitment of Healthy Participants: Controls will be recruited through word-of-mouth, and advertisement.

2. **Inclusion/Exclusion Criteria:** What are the criteria for subject inclusion or exclusion? How will eligibility be determined, and by whom?

#### Eligibility:

Eligibility will be determined by the staff consenting subjects, under the supervision of the Principal Investigator.

# **Inclusion Criteria:**

All Subjects: 1. ages 13 to 30

2. subjects from all racial and minority groups

Subjects with Mood Disorders and/or ADHD

1. subjects with Bipolar Disorder, Major Depressive Disorder, and/or Attention Deficit Hyperactivity Disorder,

**Control Subjects** 

1. no lifetime history of major Axis I disorder

Subjects in the Psychotherapy Pilot Study:

1. subjects must have a current mood disorder, be age 13-17 years old, with a current outpatient clinician.

Subjects in the BE-SMART Psychotherapy Study and Supplement:

- 1. subjects must be age 16-29 years old meeting DSM5 criteria for BDI, BDII, BD Other Specified Bipolar (BD-OS).
- 2. subjects participating in the Early Targeted Psychobehavioral Treatment for Depressed Adolescents at High-Risk for Bipolar Disorder, must be age 13-21 years old and can meet for DSM5 criteria for MDD. subjects with mood symptoms, such as Ham-D score ≥ 15 and/or for hypomania/mild mania YMRS ≥ 12.

### **Exclusion criteria:**

For all subjects to participate in the interview, genetics and scanning, subjects must not have:

- 1. diagnosis of schizophrenia
- 2. mental retardation (IQ < 70)

Subjects in the BE-SMART Psychotherapy Study:

- 1. current psychosis or substance abuse disorders in #2
- 2. alcohol/substance use may be permitted if subject does not meet for more than one DSM-5 use disorder threshold criteria, except for craving, in the past 3 months (excluding nicotine and caffeine). THC may be permitted if DSM-5 score for THC use is not severe.
- 3. Receiving structured psychotherapy (e.g. family, cognitive behavioral, interpersonal/social rhythm, dialectical), or other treatments that may affect brain functioning such as rapid transcranial magnetic stimulation and electroconvulsive therapy (ECT, excluded for if in prior 6 months); however, BE-SMART is designed to be adjunctive and subjects may continue outside treatments such as pharmacotherapy
- 4. active suicidal or homicidal ideation
- 5. Alcohol or illicit substance use in the week prior to study (excluding nicotine and caffeine and THC may be permitted). Subjects will be excluded for a positive screen with exception of THC as urine toxicology screens remain positive for up to a month after THC use, they cannot accurately reflect current use.

For Healthy Control Subjects to participate in interview, genetics and scanning, subject's must not have:

- 1. history of a mood disorder in a first-degree relative
- 2. history of prescribed psychotropic medication

## For all subjects to participate in scanning session, subjects must not have:

- i. history of structural brain disease, mass lesion, stroke or epilepsy
- ii. history of loss of consciousness greater than 5 minutes
- iii. significant medical illness e.g. insulin dependent diabetes milletus
- iv. any possibility of pregnancy
- v. presence of ferromagnetic devices e.g. pacemakers, reactive metallic implants or fragments
- vi. alcohol/substance use may be permitted if subject does not meet current DSM-5 use disorder (excluding nicotine and caffeine).

Page 15 of 28

#### APPROVED BY THE YALE UNIVERSITY IRB 6/15/2023

Principal Investigator: [name]

MAY 2023 HIC #0407026910

vii. orthodontic braces viii. history of claustrophobia

Follow-up visit:

Subjects will be instructed not to drink any alcohol or use any other substances within 1 week of the scanning session that could change brain function aside from use of their prescribed medication. They will be instructed to restrict caffeine use to 5 hours prior to scan. Subjects that smoke will be instructed to complete smoking cigarettes one hour prior to scanning and to then abstain from smoking until scanning has been completed.

3. **Subject Population:** Provide a detailed description of the proposed involvement of human subjects. Describe the characteristics of the subject population, including their anticipated number, age range and health status

The selection of subjects should be equitable. Generally speaking, subject selection should reflect a reasonable cross-section of the population that is being studied. In research that requires a more restricted population, the rationale for this need should be fully justified. Investigators must also provide scientific justification for the exclusion of underrepresented populations such as women, children, or minorities.

Subjects will be age 13 years or older but under age 31. We plan to include equal numbers of males and females (inclusion of sex assigned at birth) and minority subjects in proportions representative of the population in the greater New Haven area. However, specifically for the [name] sample, the adolescent cohort is primarily minority, with 60% African-American, 14% Hispanic, and 26% Caucasian.

There will be no increase to the target enrollment with the addition of the psychotherapy pilot study. Subjects already participating in the imaging component of the study will be invited to participate in a pilot treatment study, with an initial aim of piloting 10 subjects.

There will be an increase of 86 BD adolescent/young adult subjects to the target enrollment with the addition of the BE-SMART and Supplement. These subjects will be 16 to 30 years old at entry and will participate in open trials, 50% randomized to either the BE-SMART-DR or BE-SMART-ER. With an estimate of 20% attrition, there will be 26 completers per group. An additional 13 "at risk" for bipolar disorder adolescent subjects, who will not be randomized, but participate in the BE-SMART-DR psychotherapy.

4. **Vulnerable Subjects:** Certain populations are considered vulnerable and require special protections when asked to participate in a research study. (Vulnerable populations include, but are not limited to pregnant women, fetuses, human embryos, prisoners, children, and cognitively impaired individuals or persons with questionable capacity to consent. Others which may require special consideration include elderly persons, economically disadvantaged persons and educationally disadvantaged persons.)

Children include all persons who have not attained the legal age for consent to treatments or procedures involved in the research under the applicable law of the jurisdiction in which the research will be conducted (the age of majority is 18 years in the Connecticut). Parental permission and the child's assent are required for participation in the study. (Assent is defined as "a child's affirmative agreement to participate in research" and should be sought in addition to parental permission when the minor subject is sufficiently mature to understand the nature of his or her participation in a Research study.) Please refer to the HIC Guidelines for Investigators at

http://www.med.yale.edu/hic/forms/forms/guidelines.pdf

Will vulnerable subjects be enrolled in the study? If so, identify the vulnerable population and provide a justification for their involvement. Also, address any additional safeguards necessary to protect the rights and welfare of vulnerable subjects.

All study personnel working with this child/adolescent/adult population will have completed Good Clinical Practice trainings. Both written parental permission and the child's assent will be obtained for all minor subjects under the age of 18 who were invited to participate. Literature supports that although the age range encompasses a period of neurodevelopmental change, some subcortical system components are relatively stable by this point in development. The amygdala, a key target, has a developmental peak by age 16 years, and can be expected to be relatively stable in structure and function levels in the child/adolescent/young adults. We reported amygdala volume decreases and associated activation increases to emotional faces in adolescents with BD in this age range, considered some of the most replicated biological findings in BD. It is possible that the magnitude of target engagement could vary by age, and this would be important to study. This would be in-line with our overall program of research.

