*Hypothesis 6C:* Adolescents with high stress exposure who are 5-HTTLPR (SLC6A4) "s" carriers will show both the greatest magnitude of circuitry dysfunction and addictive behaviors.

**Exploratory Aim** #7: Investigate changes in corticolimbic system functioning during emotional regulation and to use fMRI, before, at mid-point, and after an emotional regulation intervention, to assess intervention-associated changes in AMYG and OFC responses to emotional stimuli and functional connectivity and if incorporating actigraphy, investigate objective cross-domain peripheral measures of daily rhythm regularity at high temporal resolution.

*Hypothesis 7A*: The emotional regulation psychotherapy treatment will be associated with "normalization" of the circuitry and symptom improvement.

*Hypothesis 7B*: Integrating actigraphy and EMA will provide objective and high temporal resolution data about how daily rhythm's change with BE-SMART behavioral therapies.

**Exploratory Aim #8:** Use 7T MRI and magnetic resonance spectroscopy (MRS) to investigate amygdala anatomy at high resolution and to study glutamate neurotransmitter levels in the amygdala *Hypothesis 8:* The volume of the lateral nucleus of the amygdala will be decreased, and there will be differences in amygdala glutamate levels, in adolescents with mood disorders.

2. **Background:** Describe the background information that led to the plan for this project. Please provide references to support the expectation of obtaining useful scientific data. When available, previous work in animal and/or human studies should be included.

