## **Salutary Effects of Psychotherapy:**

New treatments to help to reduce the emotional dysregulation of mood disorders are critically needed. We are continuing to study an emotional dysregulation psychotherapy treatment in which subjects learn skills to help to down-regulate maladaptive emotional responses and learn beneficial, healthy sleep and activity habits. We repeat scanning and symptom and behavioral assessments at the midpoint, and after the psychotherapy is completed. This collected information will demonstrate that the treatment can help subjects to better self-regulate their emotional responses and behaviors, reducing abnormalities in neural circuitry responses and their symptoms.

Incorporating the actigraphy device and EMA data has potential to generate novel scientific insights into the brain and behavioral mechanisms underlying beneficial effects of daily rhythm regularization on the emotional circuitry target.

3. **Research Plan:** Please provide an orderly scientific description of the study design and research procedures as they directly affect the subjects. *Please note: Investigators should take care to distinguish clearly between any procedures that are experimental and those that are part of subjects' standard clinical care.* 

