# **BE-SMART Psychotherapy Treatment**:

Subjects with or "at-risk" of mood disorders are invited to participate in the psychotherapy treatment trial. The testing assesses acceptability to subjects and ability to engage the brain targets, and the treatment will be adapted to optimize helpfulness to the subjects, as compared to burden. Subjects participating in our scanning studies frequently request opportunities to participate in treatment studies. This provides free, non-medication treatment. The treatment is overseen by a licensed mental health professional. The treatment is designed to increase healthy emotional regulation and behavioral habits (such as sleep and activity). The treatment provided in this study will be in addition to subjects' current treatment, as the study treatment is considered an adjunctive treatment.

Subjects may participate in 12 therapy sessions, at a rate of 1 session every one to two weeks. Sessions are anticipated to last about 1 hour each. These therapy sessions may be videotaped and audiotaped (only with the written consent of the subject, and when appropriate, the subject's parent or guardian). Subjects may be asked to complete weekly worksheets (either through qualtrics or by pen and paper) and practice the skills learned from these sessions and they may be asked questions about how they are feeling. There may be an interview assessment and scan performed at baseline, midpoint and at the completion of the psychotherapy sessions to review progress for the BE-SMART subjects. As it is often challenging for subjects to come to the site, we will conduct sessions by videocommunication (Zoom) and plan that approximately 50-75% of the sessions will occur via such methods.

Subjects participating in the R61 Supplement will receive the psychotherapy treatment the actigraphy and EMA electronic diary devices. We ask that subjects use the provided actigraphy device in place of any current personal activity tracker they may be using, or if not cumbersome, in conjunction with their own device for the duration of the study. The actigraph is widely used in research settings, including with our NIMH intramural collaborators on this funded Supplement with whom we will be sharing deidentified information with their computational team. The EMA electronic diary will allow us to monitor changes in subject's emotions, behavior, and activities and show us how these measures change

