# **MRI Data Processing:**

Image processing and analysis will be performed at the Yale MR Center on UNIX workstations using standard as well as locally developed software. Data are stripped of all identifying information and assigned a numerical code so that image processors are blind to subject information. Processing will include transformation of brains across subjects into common stereotactic space. Pre-existing subjects who had consented to share their samples and data may have their post processed MRI data along with de-identified information in computer files about their processed samples sent to the University of Iowa as part of a GWAS. Yale is not receiving information from University of Iowa for this study.

- **4. Statistical Considerations:** Describe the statistical analyses that support the study design. This section should include:
  - The number of subjects expected to enter the study.
  - A statement about the statistical power of the study to test the major hypothesis.
  - A summary of the plans for data analysis.

Hypothesis testing will be performed with region of interest measures as the dependent variables, analyzed in mixed models in consultation with a statistician, e.g. with current collaborators such as [name] (EPH) and [name] (GCRC). For example, to test hypothesis #1: diagnosis will be the between subject's variable. Hemisphere (right vs. left) and time (1st scan vs. 2nd scan) will be the within-subject variables and there will be a random subject effect. Repeated measures will be performed over the spatial domain of hemisphere. Total brain volume will be included as a covariate to control for general scaling effects. Terms that are not significant (p>0.05) will be eliminated via a backward stepwise algorithm, with the constraint that the model at each step is hierarchically well-formulated. Least squares means (Is means) and standard errors (SE) will be calculated in the mixed model and plotted to interpret significant interactions.

Whole brain analyses will also be performed to examine for group differences in regions not hypothesized *a priori*. These will be performed with widely available software such as SPM software as well locally developed software.

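### BE-SMART randomises bipolar participants to DR or ER, but no aim, model or precision statement uses the allocation, and the completer count does not follow from the 86 subjects beside it

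*Combined protocol and SAP*

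**What the plan says.** - **Allocation.** Section V item 3 (Subject Population) adds 86 bipolar participants who "will participate in open trials, 50% randomized to either the BE-SMART-DR or BE-SMART-ER". It expects 20% attrition and 26 completers in each group. Section II item 5 splits the 86 into 66 under the R61 grant and 20 under its Supplement. A further 13 at-risk participants are not randomised and receive DR.
- **Aim.** Exploratory Aim #7 uses fMRI "before, at mid-point, and after an emotional regulation intervention, to assess intervention-associated changes in AMYG and OFC responses to emotional stimuli", and also functional connectivity. Hypothesis 7A links the therapy, treated as a single entity, to circuitry normalisation and symptom improvement. Hypothesis 7B concerns daily rhythms. Neither mentions two arms.
- **Model.** Section III item 4 sends region-of-interest measures to mixed models. Its only worked example is "to test hypothesis #1: diagnosis will be the between subject's variable", with two scan times. Terms with p>0.05 are removed by backward elimination.
- **Power.** "A sample size of 50 subjects per group will provide >95% power to detect differences of this magnitude" refers to bipolar versus healthy volume differences.
- **Background.** Section III item 2, under Salutary Effects of Psychotherapy, says of the repeat scans and ratings: "This collected information will demonstrate that the treatment can help subjects to better self-regulate their emotional responses and behaviors".
- **Co-treatment.** The BE-SMART exclusions cover "Receiving structured psychotherapy (e.g. family, cognitive behavioral, interpersonal/social rhythm, dialectical), or other treatments that may affect brain functioning", but the same item lets outside pharmacotherapy continue.

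**The concern.** The DR/ER allocation is the only randomised comparison that the documents describe, and it has no stated analytic use. Followed as written, the psychotherapy results would rest on change over time within participants. The arm comparison would either be left out, or its outcome and time point would be picked once the data were visible.

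The background sentence raises the stakes because it announces a conclusion about benefit. Change from baseline to end of therapy mixes any therapy effect with medication changes, natural course, regression of symptoms from an elevated starting point, and familiarity with the scanner task. No untreated or healthy group is described as re-scanned on the therapy schedule to separate these.

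The one figure tied to the allocation, 26 completers per group, also does not follow from the total in its own paragraph. The size of the randomised comparison is therefore unclear.

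**Working it through.** **1. Where the arm appears.**

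| Place | Between-subject factor | Times | DR/ER term |
|---|---|---|---|
| Exploratory Aim #7, H7A, H7B | none | before, mid-point, after | none |
| Section III item 4, worked example | diagnosis | two scans | none |
| Power | bipolar vs healthy | not applicable | none |
| Section V item 3 | DR vs ER | not given | head count only |

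If the backward elimination rule were carried over to Aim #7, a non-significant arm term would be deleted instead of estimated.

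**2. The plan's power figure.** Inputs from the Power text are d = 0.93, 50 per group and 30% attrition, so 35 per group. Two-sided 5% is assumed. The normal approximation gives 97.3% and the t-test 97.0%. The claim of more than 95% reproduces, but for diagnosis groups only.

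**3. The completer count.** Completers per arm = N x (1 - 0.20) / 2.
- N = 66: 66 x 0.8 / 2 = 26.4, which matches the stated 26.
- N = 86: 86 x 0.8 / 2 = 34.4, which does not.
- Conversely, 52 completers (2 x 26) is attrition of 14/66 = 21.2% from 66, but 34/86 = 39.5% from 86.

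**4. What a DR versus ER contrast could resolve.** The documents give no effect size, so these are detectable standardised differences at 80% power and two-sided 5%. Unadjusted: two-sample t, df = 2n - 2, noncentrality d x sqrt(n/2). Baseline-adjusted: residual SD multiplied by sqrt(1 - rho^2), df = 2n - 3. The baseline correlation rho is assumed.

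| Completers per arm | Unadjusted | rho 0.3 | rho 0.5 | rho 0.7 |
|---|---|---|---|---|
| 26 | 0.79 | 0.76 | 0.69 | 0.57 |
| 34 | 0.69 | 0.66 | 0.60 | 0.49 |

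95% CI half-width with 26 per arm = t x sqrt(2/26) x sqrt(1 - rho^2), where sqrt(2/26) = 0.277:
- unadjusted: 2.009 x 0.277 = 0.56 SD;
- adjusted: 0.53, 0.48 and 0.40 SD at rho 0.3, 0.5 and 0.7.

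**5. Room for choice after the data are seen.** Aim #7 and H7A name four outcome families (amygdala response, OFC response, functional connectivity, symptoms). With two post-baseline times that makes 4 x 2 = 8 possible arm contrasts. If all eight were searched, were independent, and there were no true difference, the chance of at least one p<0.05 would be 1 - 0.95^8 = 0.34. Correlation lowers it: 30%, 25% and 19% by simulation at assumed pairwise correlations of 0.3, 0.5 and 0.7.

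**The case against.** The best defence is that Aim #7 is exploratory, the trials are called open, and the stated purpose is modest: "The testing assesses acceptability to subjects and ability to engage the brain targets". Within-person change serves that purpose. The therapy is also to be adapted as testing proceeds, which would blur an arm contrast. H7A claims only an association. The mixed-model sentence is general, and Hypothesis 1 is offered only as an example. Section V item 4 expects the amygdala to be fairly stable at these ages, so maturation may explain little of any change. All of this stands. It removes the need for a formal power calculation and lowers the weight of the point. It does not say what the randomisation is for, and it makes the background sentence harder to defend. Amygdala stability also does not exclude medication changes, task familiarity or symptom regression.

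A reader might infer more than the documents support:

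- **That both arms are active versions, or that the study has no control.** BE-SMART-ER appears once and is not defined. It could be an alternative therapy or a comparator. Only the wording of Aim #7 and of the background lacks a comparator.
- **That the assessment times are not fixed.** Section III item 3 does say "There may be an interview assessment and scan performed at baseline, midpoint and at the completion of the psychotherapy sessions". But Aim #7, the Salutary Effects text and the three-part payment schedule in Section VIII item 2 all give three time points, and participants may choose which parts to join. This is loose wording.
- **That 26 per group is wrong.** It is right if only the 66 R61 participants are randomised.
- **That a 34% false-positive risk is expected.** It applies only if someone searches eight independent contrasts, and no such search is planned.

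**Conclusion.** The concern holds as a minor to moderate point. A randomised allocation is described, and no aim, hypothesis, model or precision statement uses it. The background sentence promises a conclusion about benefit that open within-person change with continuing pharmacotherapy cannot deliver, even though structured psychotherapy and some other treatments are excluded.

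The sample statement must be reconciled: 26.4 per arm comes from 66 and 34.4 from 86, and the text does not say whether the 20 Supplement participants are randomised.

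The conclusion rests on reading the allocation as equal halves, which the wording leaves loose but the equal completer counts support. The precision figures assume two-sided 5% testing and the stated baseline correlations. What the contrast could say about H7A cannot be settled until ER is defined.

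**What to change.** 1. **Define BE-SMART-ER and add the contrast to Aim #7.** Specify an exploratory DR versus ER comparison in all randomised participants: a baseline-adjusted mixed model over midpoint and end, with arm, time and arm x time, using partial data. Exempt the arm terms from backward elimination if that rule is applied here. Name one lead outcome and time point in advance (for example, amygdala response to emotional faces at end of therapy), make the rest secondary, and report the estimate with its 95% CI. State what the contrast can show about H7A given the definition of ER, without presuming that both arms are active.
2. **Soften the background sentence.** The data will *assess whether* treatment helps. Report within-arm change, and change in the non-randomised participants, as descriptive target engagement.
3. **Reconcile the randomised number.** If only the 66 are randomised, say so and keep 26 per group. If all 86 are, restate about 34 per group.
4. **Wording clean-up.** Align the permissive sentence on assessments in Section III item 3 with the three time points given elsewhere.

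The cost is text only, since the payment schedule already covers interviews and MRI at all three parts. The downsides are limited precision, as shown in the working, and that outcomes other than the lead become secondary.
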